7.1.4 Unanticipated Problems

In line with the OHRP definition, unanticipated problems include any incident, experience, or outcome that meets **all** of the following criteria:

1. unexpected (in terms of nature, severity, or frequency) given (a) the research procedures that are described in the protocol-related documents, such as the IRB-approved research protocol and informed consent document; and (b) the characteristics of the subject population being studied;
2. related or possibly related to participation in the research (in this guidance document, *possibly related* means there is a reasonable possibility that the incident, experience, or outcome may have been caused by the procedures involved in the research); and
3. suggests that the research places subjects or others at a greater risk of harm (including physical, psychological, economic, or social harm) than was previously known or recognized.

7.2 Reporting Procedures

7.2.1 Adverse Events

Any adverse events are reported to the DSMB at each meeting and to the NCH IRB annually.

7.2.2 Serious Adverse Events

The DSMB is notified of any serious adverse events determined to be related to the intervention and are unexpected within 5 business days of discovery. Other serious adverse events are reported to the DSMB at each meeting.

Similarly, and per the NCH HRP-103 (updated 12/10/2018), serious adverse events determined to be related to the intervention and are unexpected are reported to the NCH IRB within 5 business days of discovery. Other serious adverse events are reported to the NCH IRB annually.

Serious adverse events that are fatal or life-threatening and are unexpected are reported to NHLBI within 7 calendar days of discovery by the investigator. For non-fatal, non-life-threatening unexpected, serious adverse events, NHLBI is notified within 15 calendar days, by the investigator.

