5.3.4 Termination of Study

Because the AHA and American College of Cardiology indicate that receiving an exercise stress test is a standard of care and that CHD survivors with moderate to complex disease should be engaged in routine PA as long as it is deemed safe,⁷ termination of the study due to the development of adverse events is not anticipated. There are several procedures aimed to rule out any participants who may be at an increased risk of an adverse event due to the intervention. First, participants' cardiologists are asked about the eligibility of each potential participant. Second, participants undergo a baseline exercise stress test, in part, to rule out any cardiovascular contraindications for PA. If limitations in PA exist, these are incorporated into the exercise prescription developed by the exercise physiologist who conducted the stress test/principal investigator in consultation with the study physician, and the PA coaches work with participants on PA within the parameters of the exercise prescription. Participants' cardiologists have access to the results of the stress test, which are posted in participants' electronic medical record. However, the study will be terminated if the Data Safety Monitoring Board (DSMB) or IRB concludes, based on their findings, that termination is in the best interest of the participants.

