7 ASSESSMENT OF SAFETY

7.1 Methods and Timing for Assessing, Recording, and Analyzing Safety Parameters

7.1.1 Adverse Events

Definition

For the current study, an adverse event is an unanticipated change in cardiovascular, musculoskeletal, or emotional symptoms that are (1) concerning to the participant and (2) results in seeking medical attention, if cardiovascular or musculoskeletal in nature. Any condition that is present at the time that the participant is screened will be considered as baseline and not reported as an adverse event. However, if the study participant's condition deteriorates at any time during the study, it will be recorded as an adverse event. Serious adverse events are defined as adverse events that are severe in classification (as described below). We do not anticipate any serious adverse events due to study procedures. Adverse events that occur for participants during the course of the study are comprehensively documented, including events during the stress test, symptoms reported during the course of the intervention from participants in the intervention arm, dates and reasons for pauses in the study protocol due to symptom reporting, and determination of ability to proceed by participants' cardiologists. All unscheduled cardiology outpatient visits, visits to urgent care or the emergency department, unscheduled hospitalizations, or any other changes in health are documented. Participants in the comparison arm are asked whether they sought medical attention in the aforementioned contexts during the interim and post-intervention questionnaires. Additionally, the occurrence of any adverse event or serious adverse event may come to the attention of study staff during other study contacts (e.g., intervention meetings).

Classification

All adverse events and serious adverse events will be assessed by the PI and the study physician, [name], according to the guidelines outlined here.

Severity: The following guidelines will be used to describe severity:

- Mild: Events require minimal or no treatment and do not interfere with the participant's daily activities.
- Moderate: Events result in a low level of inconvenience or concern with the therapeutic measures. Moderate events may cause some interference with functioning.
- Severe: Events that require in-patient hospitalization and/or resulted in death or permanent disability.

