7.2.3 Unanticipated Problems

Any unanticipated problems that are not serious adverse events will be reported to the DSMB within 2 weeks and to NHLBI within 14 days by the investigator. If an unanticipated event *is* considered a serious adverse event, the aforementioned reporting time for serious adverse events will be followed.

7.3 Type and Duration of Follow-up of Subjects after Adverse Events and Unanticipated Problems

Participants will be monitored for adverse events and unanticipated problems from the start of the intervention in Phase 2 until the post-intervention assessment that occurs 22 weeks after the start of the intervention, as this signifies study completion. Adverse events and unanticipated problems will be followed until stabilization or resolution, or 30 days after study completion (whichever occurs sooner).

All cardiac-related adverse events and unanticipated problems are discussed with the cardiology medical team. The cardiology medical team determines whether participation in the study is suspended, and for how long, or terminated.

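### An unexpected serious adverse event graded not related reaches NHLBI in 7 or 15 days but the DSMB only at its next meeting, and section 7.2.3 names no IRB route for non-serious unanticipated problems

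*Combined protocol and SAP*

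**What the plan says.** Section 7.2.2 uses two different triggers.

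- **NHLBI:** the clock depends on expectedness alone. "Serious adverse events that are fatal or life-threatening and are unexpected are reported to NHLBI within 7 calendar days of discovery by the investigator". Other unexpected SAEs go to NHLBI within 15 calendar days.
- **DSMB:** fast notice also needs a finding of relatedness. "The DSMB is notified of any serious adverse events determined to be related to the intervention and are unexpected within 5 business days of discovery". For everything else, "Other serious adverse events are reported to the DSMB at each meeting".
- **NCH IRB:** the same two-part trigger and the same 5 business days, with the timing attributed to an institutional policy (HRP-103). For the rest, "Other serious adverse events are reported to the NCH IRB annually".

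Section 7.1.1 says who makes the grade: "All adverse events and serious adverse events will be assessed by the PI and the study physician". Section 7.4 calls an ad hoc meeting with the DSMB once an unexpected SAE is found to be related to the intervention. Section 5.3.4 places the power to end the trial with two bodies: "the study will be terminated if the Data Safety Monitoring Board (DSMB) or IRB concludes" that this best serves participants. Section 7.5 promises the DSMB bi-yearly reports and does not define the term.

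For unanticipated problems, section 7.2.3 reads: "Any unanticipated problems that are not serious adverse events will be reported to the DSMB within 2 weeks and to NHLBI within 14 days". The IRB is not named there. Unanticipated problems that are also SAEs follow the SAE timelines.

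**The concern.** The relatedness grade decides two things at once: whether the DSMB hears quickly, and whether the halting step in 7.4 opens. If the PI and study physician grade an unexpected death as not related, no rule brings it to the DSMB before its next meeting. The funder already holds a report of it. NHLBI is not named in 5.3.4 as a body that can terminate the study, and nothing in the protocol says it passes reports on.

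Causality is often least clear in the events where the grade matters most. These participants have moderate or complex congenital heart disease, so underlying disease will often be a plausible alternative cause. A DSMB is there to give an independent second look at that judgement. Under the present text the look may come months later, while baseline stress tests and randomization continue.

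The IRB gap in 7.2.3 is separate and smaller. By the definition in 7.1.4, an unanticipated problem is unexpected, at least possibly related to the research, and suggests more risk than was known. Section 7.2 gives no route or time for telling the IRB of one that is not an SAE.

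**Working it through.** The plan states no delay figure to reproduce. The check sets the routes side by side and then converts them to days.

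**Step 1. Routes in 7.2.2 and 7.2.3**

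| Event | NHLBI | DSMB | NCH IRB |
|---|---|---|---|
| Unexpected SAE, graded related | 7 or 15 calendar days | 5 business days | 5 business days |
| Unexpected SAE, graded not related | 7 or 15 calendar days | next meeting | annually |
| Unanticipated problem, not an SAE | 14 days | 2 weeks | not named |

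**Step 2. Related unexpected SAE.** Five business days from a weekday discovery span one weekend: 5 + 2 = 7 calendar days. Discovery on a Saturday gives 6 and on a Sunday 5. One public holiday raises the maximum to between 8 and 10, depending on the day of discovery. For a fatal event NHLBI's limit is 7. The three bodies hear at about the same time, so there is no gap in this row.

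**Step 3. Unexpected SAE graded not related: DSMB.** Assume bi-yearly means twice a year and that meetings follow the reports.

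- Longest wait: 365.25 / 2 = 182.6 days, about 26 weeks.
- Lag behind NHLBI, fatal or life-threatening event: 182.6 − 7 = 175.6 days.
- Lag behind NHLBI, other unexpected SAE: 182.6 − 15 = 167.6 days.
- Average wait, if events fall evenly between meetings: 182.6 / 2 = 91.3 days, about 13 weeks.
- If bi-yearly meant every two years, the longest wait would be 2 × 365.25 = 730.5 days, the whole planned study duration.

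**Step 4. Same event: IRB.** The longest wait is 365.25 days, which is 365.25 − 7 = 358.25 days behind NHLBI for a fatal event.

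**Step 5. Activity during the longest DSMB wait.** Inputs are up to 90 Phase 1 participants and 40 randomized over 2 years (104 weeks), with even accrual assumed.

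- Baseline stress tests: 90 × 26 / 104 = 22.5.
- Randomizations: 40 × 26 / 104 = 10.

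**Step 6. Unanticipated problem, not an SAE.** Two weeks equals 14 days, so the DSMB and NHLBI share one limit. Only the IRB is missing.

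**The case against.** The strongest reply is that the gap is narrow and partly covered elsewhere. Much of that stands.

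- **A reader might infer that any unexpected death reaches the DSMB and IRB late.** The text does not support this. Related unexpected SAEs go to both within 5 business days (Step 2). The definition of related in 7.1.1 is also broad, since timing alone can satisfy it. It does not close the gap, because the same section lets an established alternative cause support a grade of not related, and one event can meet both descriptions.
- **A reader might infer that nobody reviews the grade.** Section 7.3 has all cardiac-related adverse events discussed with the cardiology team, whatever the grade, and that team decides on suspending or ending participation. This is real review beyond the two graders. It is not DSMB review, and it covers cardiac events only.
- **A reader might infer that the graders judge their own exercise prescription.** Section 4 gives that task to the PI, in consultation with the study physician, only when the exercise physiologist is unavailable.
- **A reader might offer a privacy breach as an event with no route to the IRB.** This is a weak example. Loss of confidentiality is a risk already named in 2.3.1, so an ordinary breach may not count as an unanticipated problem. Section 11.5 also sends protocol deviations to the IRB.
- **The IRB timing rests on a policy not in the documents.** Section 7.2.2 cites HRP-103 for SAEs. Whether it also covers unanticipated problems cannot be judged here. Asking for faster IRB reports of unrelated SAEs would depart from timing the protocol attributes to that policy, and this point does not ask for it.

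**Conclusion.** The point holds for one class of event: an unexpected SAE, including a death, that the PI and study physician grade as not related. NHLBI hears within 7 or 15 calendar days, the DSMB at its next meeting and the IRB annually. The DSMB therefore cannot promptly check the grade on which the 7.4 halting step depends.

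The 26-week figure is a worst case. It assumes an event just after a meeting, bi-yearly read as twice a year, and meetings that follow the reports; under the same reading the average wait is about 13 weeks. The 22.5 stress tests and 10 randomizations further assume even accrual, which the COVID-19 cancellations in section 14 make doubtful. They are avoidable exposure only if the grade of not related was wrong, and the documents give no basis for a probability of that.

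It would go too far to say that the bodies able to stop the study always learn last. That is untrue of related unexpected SAEs, and untrue of the DSMB for unanticipated problems that are not SAEs. The IRB omission in 7.2.3 is likewise confined to those non-SAE problems.

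This is a modest gap in safety oversight, worth correcting because the correction is nearly free.

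**What to change.** In 7.2.2, send the DSMB a copy of every unexpected-SAE report made to NHLBI, on the same 7- or 15-calendar-day clock, with the PI and study-physician causality grade attached. Keep the 5-business-day route to the DSMB and IRB for related unexpected SAEs. Leave expedited IRB reporting of unrelated SAEs to the institutional policy.

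In 7.2.3, add the NCH IRB as a recipient of unanticipated problems that are not SAEs, within the same 14 days and subject to that policy.

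The cost is amendment wording and a few extra submissions. The NHLBI report is prepared in any case, and section 7.1.1 anticipates no SAEs due to study procedures. No treatment, assessment or analysis changes.

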7.2.3 Unanticipated Problems

Any unanticipated problems that are not serious adverse events will be reported to the DSMB within 2 weeks and to NHLBI within 14 days by the investigator. If an unanticipated event *is* considered a serious adverse event, the aforementioned reporting time for serious adverse events will be followed.

7.3 Type and Duration of Follow-up of Subjects after Adverse Events and Unanticipated Problems

Participants will be monitored for adverse events and unanticipated problems from the start of the intervention in Phase 2 until the post-intervention assessment that occurs 22 weeks after the start of the intervention, as this signifies study completion. Adverse events and unanticipated problems will be followed until stabilization or resolution, or 30 days after study completion (whichever occurs sooner).

All cardiac-related adverse events and unanticipated problems are discussed with the cardiology medical team. The cardiology medical team determines whether participation in the study is suspended, and for how long, or terminated.

7.4 Halting Rules

If it is found that the study intervention is related to an unexpected serious adverse event, an ad hoc meeting will commence that will include the PI, study physician, and the DSMB to determine if enrollment needs to be temporarily suspended until a safety review is convened. If a safety review is conducted, the DSMB will decide whether the study should continue per protocol, proceed with

caution, be further investigated, be discontinued, or be modified and then proceed. Suspension of enrollment (for a particular group or for the entire study) is another potential outcome of a safety review.

7.5 Safety Oversight

Safety oversight of this study is under the direction of the study PI, NCH IRB, as well as a DSMB. The DSMB consists of two faculty members from NCH and a faculty member from the University of Notre Dame. [name] [name] is a dual-boarded pediatric and adult congenital cardiologist housed in the Heart Center at NCH. [name] is a board-certified pediatrician and a former Director of the Division of Epidemiology, Statistics, and Prevention Research at the National Institute of Child Health and Human Development. [name] has been involved as a Co-I of multiple RCTs and currently serves on the DSMB for an NIH-funded clinical trial. [name] is a Professor in the Department of Psychology, an Associate Dean for Faculty and Research in the Mendoza College of Business at the University of Notre Dame, and is an accredited professional statistician per the American Statistical Association. [name] currently serves on several DSMBs for NIH-funded clinical trials. The NCH IRB has reviewed and approved the Data and Safety Monitoring Plan for this study. Bi-yearly reports summarizing the number of participants enrolled, the number of stress tests completed, the number of abnormalities detected during exercise stress testing, adverse events and serious adverse events, and the number of participants who have contacted their cardiologists due to concern over symptoms while engaged in the treatment arm will be provided to the DSMB. This summary is submitted to the IRB with the annual review.

7.6 Study Hypotheses

Hypothesis 1: Young adults are hypothesized to rate the intervention as enjoyable, easy, relevant, and useful.

7.7 Sample Size Considerations

The sample size of 40 for the Phase 2 RCT component is obtainable in the 2-year timeframe of this study and is adequate for addressing the study aims for determining feasibility (i.e., intervention acceptability, recruitment rate, retention rate, intervention session adherence, and assessment completion rate). The current sample size is not powered to detect treatment effects and is not

intended to be used for effect size estimation due to the risk of under or overestimating the sample size for the larger study^{62,63}.

Planned Interim Analyses (if applicable)

No interim analysis is planned.

7.8 Analysis Plan

Aim 1: Evaluate the feasibility of the intervention.

Objective indicators of feasibility will be evaluated, including recruitment rate (# recruited divided by # approached), adherence to intervention sessions (% sessions completed per participant), retention rate (# drop outs divided by # randomized) and assessment completion rate (% of participants who completed each assessment and the timeframe in which completed). Participants will also rate the intervention on multiple dimensions, and mean/median ratings will be computed.

Aim 2: Obtain qualitative feedback on session content and study procedures from participants using focus groups.

Focus group feedback will be transcribed and coded. Themes will be identified using 2 coders, and the number of participants who endorse a theme will be tabulated.

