3 OBJECTIVES

3.1 Study Objectives

A total of up to 90 young adults (ages 18 -25) are anticipated to be enrolled in Phase 1 of the study, which establishes eligibility for Phase 2. For Phase 2, the randomized trial portion of the study, we plan to enroll a total of 40 young adults. The aims of the study are to:

1. *Aim 1:* Evaluate the feasibility of the intervention.
Hypothesis 1: Young adults will rate participating in the intervention as enjoyable, easy, relevant, and useful.
2. *Aim 2:* Obtain qualitative feedback on session content and study procedures from participants using focus groups.

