5.3.2 Reasons for Withdrawal

Study participation is discontinued under the following circumstances:

- If participant's cardiologist determines that he/she is no longer eligible for the study due to a change in his/her cardiac condition.
- The participant requests withdrawal from the study.
- Development or reveal of any exclusion criteria (e.g., need for cardiac surgery).

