5.3.3 Handling of Withdrawals

If withdraw occurs because a participant's cardiologist determines that the participant should no longer be in the study due to a change in medical status or the participant requests to be withdrawn, participants are asked to complete the assessments if possible and are included in intent-to-treat analyses.

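### Section 7.8 defines the retention rate as drop-outs over randomised, which is the drop-out rate, the complement of retention

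*Combined protocol and SAP*

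**What the plan says.** Aim 1 in section 3.1 is to "Evaluate the feasibility of the intervention". Section 7.7 justifies the size of the randomised phase on that basis. It opens with "The sample size of 40 for the Phase 2 RCT component" and calls that number adequate for "determining feasibility (i.e., intervention acceptability, recruitment rate, retention rate, intervention session adherence, and assessment completion rate". It gives no formula and no target for any of these measures.

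The formulas are in section 7.8. Retention is given there as "retention rate (# drop outs divided by # randomized". The same sentence defines recruitment as the number recruited over the number approached, session adherence as "adherence to intervention sessions (% sessions completed per participant", and assessment completion as "assessment completion rate (% of participants who completed each assessment and the timeframe in which completed".

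Sections 5.3.2 and 5.3.3 deal with withdrawal but define no rate.

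**The concern.** The label and the formula in 7.8 describe opposite quantities. Recruitment, adherence and completion all rise as feasibility improves. Retention, as defined, falls.

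The trial is expressly not powered for treatment effects, and section 2.2 says its pilot data are to shape the next phase of investigation. The feasibility indicators are therefore a main product of the study. If the ratio is reported under its present name, a well-retained trial will appear to have lost most of its participants, and a poorly retained one will look good. Someone planning the larger trial from the labelled percentage alone would read it the wrong way round.

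**Working it through.** The documents state no retention or drop-out figure, so there is nothing to reproduce. The check is of the definition itself.

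**Inputs**
- N = 40 randomised, the planned number in section 7.7.
- D = number of drop-outs. The documents give no expected value, so the values below are assumptions chosen to show the range.

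**Formulas**
- Section 7.8 as written: D / N
- Retention: (N − D) / N = 1 − D / N
- Difference, retention minus the stated ratio: (N − 2D) / N

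**Results for N = 40**

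| D (assumed) | 7.8 formula, D/40 | Retention, (40 − D)/40 | Difference (percentage points) |
|---|---|---|---|
| 0 | 0% | 100% | 100 |
| 4 | 10% | 90% | 80 |
| 8 | 20% | 80% | 60 |
| 20 | 50% | 50% | 0 |

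The two columns sum to 100% in every row, so the stated ratio is exactly the complement of retention. They agree only at D = N/2 = 20, when half the sample has left.

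**Is it corrected elsewhere?** Section 7.7 uses the term without a formula. Section 5.3.2 lists reasons for ending participation, and section 5.3.3 says how withdrawals are handled. Neither gives a competing definition, so 7.8 is the only one and it is current text.

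**The case against.** The strongest reply is that almost nothing turns on this. The formula is printed beside its label, so an analyst holding both counts would probably notice the inversion. No progression threshold, hypothesis test or sample-size calculation uses the rate. Hypothesis 1 and the primary outcome in section 3.2.1 concern participants' ratings of the intervention. All of this is correct, and it is why the point is minor. It does not make the definition right. Nor is the intention settled by the text, since the authors could have meant either retention or drop-out.

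A second reply is that the differences in the table are a property of any complement and do not estimate likely misreporting. That is also fair. They show what the rule returns if followed and reported under its label. They do not predict a bias of that size.

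A third point is that retention is the exact complement only if everyone is either a drop-out or retained, and the plan does not define a drop-out. Under section 5.3.3, people withdrawn by their cardiologist or at their own request are not simply lost: "participants are asked to complete the assessments if possible and are included in intent-to-treat analyses". Someone could stop the intervention and still be assessed. This stands as a separate gap. It means the corrected formula still needs a rule for who counts as a drop-out, but it does not rescue the present wording.

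**Conclusion.** The error is real and minor. Section 7.8 attaches the name retention to the drop-out proportion, and nothing else in the documents puts it right. With 40 randomised, complete retention would be reported as 0%; an assumed 8 drop-outs would be reported as 20% when retention is 80%. That the two quantities are complements follows from the definition and needs no assumption beyond each randomised participant being classed as either dropped out or retained. The worked percentages also rest on the planned 40 and on illustrative drop-out counts. The harm is confined to one misreported Aim 1 indicator, recoverable by subtraction.

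**What to change.** In section 7.8, make one of two changes:

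- define the retention rate as (number randomised − number of drop-outs) / number randomised; or
- keep the present ratio and rename it the drop-out rate. In that case, align the name in section 7.7 or state there that retention is one minus this rate.

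The cost is one line of wording. Both counts are already named in the current formula, so no new data are needed.

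It would also help to say in a sentence who counts as a drop-out. A bare cross-reference to section 5.3.2 would not be enough, because its list of reasons does not mention loss to follow-up, and people who simply stop responding could then be counted as retained. This addition is optional, and the main correction does not depend on it.
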